- I. **Dependent Measures**. The purpose and timing of assessments are shown in **Table 1**. Assessments will be presented via computer whenever possible with responses entered directly into the computer (with paper copies as backup in case of computer malfunction or unavailability). If an assessment is missed at any time point, whether due to participants missing appointments, glitches with computer or staff error, the assessments will be completed at the next earliest visit as possible and appropriate. If not, the assessment will be considered missed.
- The primary outcome measure is illicit opioid use (typically obtained thrice weekly during weeks 1-4, weekly during weeks 5-12, and once at the week 16 follow-up interview, biologically verified by the Redwood Toxicology Laboratory and/or Lochness Medical Supplies dipstick and/or EMIT assay). Secondary outcomes include craving ratings, retention, self- and observer-rated opioid withdrawal symptoms, adverse events, sleep quality, withdrawal signs (blood pressure, body temperature), mood, heart rate variability (HRV), decision making, and prescription opioid and other drug use, including alcohol, tobacco and caffeine. We chose assessment techniques as recommended in NIDA's A Diagnostic Source-book for Drug Abuse Treatment and Research to use comparable assessments by different investigators in substance abuse [138]. Our set of screening instruments will provide general patient information, including demographic data; medical history; and history of substance use, family substance abuse, and psychiatric treatment [130, 131]. Other assessments include the following: **1) Weekly Drug Use** (done weekly), which uses a timeline recall method that we developed in previous studies to assess self-reported use of opioids and other drugs [130, 131]; **2) PRISM 5** (done at intake or during week 1), a computerized structured clinical interview (software package will be purchase) from completed to determine several DSM-V psychiatric diagnoses [139, 140]; **3) Medication Side Effects Checklist** (done weekly), consisting of multiple items describing side effects specific to GBP, BUP or NTX [141] rated on a scale from 0 (not at all) to 4 (very much); **4) Subjective Opiate Withdrawal Scale (SOWS)** (done thrice weekly during weeks 1-3, daily (5 days) during week 4, and weekly thereafter), consisting of 16 items describing possible opioid withdrawal symptoms that are rated on a scale from 0

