For data during the BUP taper (weeks 2-3), dependent variables obtained at several time points (e.g., urine sample results for opioids, opioid withdrawal symptoms scores) will be entered into random regression models, also known as hierarchical linear models (HLMs), to determine whether scores change differentially across treatment groups [154, 155]. Continuous data will be analyzed longitudinally with MIXREG, an HLM modeling program for continuous measures [156]. Dichotomous urine results (i.e., negative or positive) will be analyzed longitudinally using the SAS procedure GLIMMIX, which allows an HLM modeling program for ordinal outcome measures [157]. We will use all available data in our analyses and will make no attempt to interpolate missing data. HLM methodologies fit a regression line for each participant, effectively interpolating missing data, before deriving final estimates. This approach of modeling repeated measures is specifically designed for use in repeated measures designs with missing data, allowing for intra-participant serial correlation and unequal variance and covariance structures over time. These problems, common to clinical trial data, are solved by incorporating available trend data for each individual with information on the behavior of the group from which the participant is drawn. If there are any significant baseline differences, the variable will be added as a cofactor in the HLM analyses. We will examine differences in retention using Kaplan-Meier Survival Analysis. Analyses will be done on those who participated long enough to start the BUP taper, as well as during GBP induction to detect possible differential dropout before the taper. To determine whether treatment group differences occurred in 1) success of retention from the BUP detox to the NTX transition and 2) eligibility to undergo oral NTX induction, we will build 2 X 2 contingency tables using percentages of participants in the GBP vs. placebo groups who 1) return on day 1 of week 4 versus drop out after completing the taper, and 2) test negative versus positive for opioids. The type, severity, and frequency of adverse events will be compared across groups. All analyses will employ a significance level of $\alpha = 0.05$, and all tests are two-tailed.

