Specific Aim 2: Acceptability and feasibility of outpatient transition to and maintenance on depot NTX therapy. Because there are two phases to NTX therapy transition (i.e., 4-day oral induction and up to 8-week depot NTX), data obtained during these phases will be analyzed separately. For the oral NTX induction, descriptive statistics will be used to report the percentage of abstinent participants who receive the 4-day oral dosing. Urine data collected each day during the 4-day induction will be entered into random regression models similar to those above to determine whether changes in illicit opioid or other drug use occurred over time. To obtain pilot data on the association between treatment group (GBP vs. placebo) and successful induction, data regarding the percentage of those receiving oral NTX and the NTX injection or not in the GBP vs. placebo groups will be entered into a 2 X 2 contingency table. The type, severity, and frequency of opioid withdrawal and/or adverse events will be compared across groups. Reasons for not receiving the NTX injection will be summarized.

For the NTX phase (weeks 4-12), dependent variables obtained at weekly time points (e.g., urine sample results for opioids and other drugs, side effect scores, opioid withdrawal scores, etc.) will be entered into random regression models (HLMs) to determine whether scores change differentially over time [154, 155]. Continuous data will be analyzed longitudinally with MIXREG [156]. Dichotomous urine results (i.e., negative or positive) will be analyzed longitudinally using the SAS procedure GLIMMIX [157]. We will examine differences in study dropout during this phase using Kaplan-Meier Survival Analysis. Our principal analyses will be done on those who participated long enough to start the depot NTX therapy. The type, severity, and frequency of adverse events will be recorded and summarized.

Specific Aim 3: Identify prognosticators of treatment outcomes. Predictors of treatment efficacy during each phase will be examined using baseline assessments (e.g., sex, level of opioid use, distress tolerance

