Sample Size. PASS (Power Analysis & Sample Size) Software was used to estimate power. Sample size for the intent-to-treat sample was determined based on having enough power during and immediately following the BUP taper to detect group differences in the primary outcome of illicit drug use and identify potential prognosticators. Based on the proportion of participants in the GBP versus placebo groups having opioid-free urines on the last day of the BUP taper from our pilot trial with GBP [31, 129], treating the one missing value as positive, a difference in the percentage of participants with opioid-free urines at the end of detox as well as immediately prior to initiating NTX therapy will be detected with >90% power with an analysis sample size of 106 total participants anticipated to remain for NTX transition. Thus, our sample size is adequate to detect differences for our primary outcome during and immediately following the detoxification. Meanwhile, there has been minimal, if any, study of sex (or other bivariate prognosticator) differences for the effect of an adjunct medication for opioid dependence, much less for prescription opioid dependence. This study will provide unique data to quantify a potential difference. Given our expected sample size of 150 participants entering the BUP detox phase, the study will have >80% power for an effect size of 0.29 (small effect size), and 106 participants eligible for NTX transition will have >80% power to detect an effect size of 0.35 (considered a "medium" effect size).

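### Pre-treatment opioid use is collected but not prespecified as a covariate in the Aim 1 arm comparisons; adjustment is left to the data or to exploratory models

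*SAP*

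**What the plan says.** **Analysis.** The SAP (Data Analysis Methods) declares as primary the course of opioid-positive urines across the detox phase. Specific Aim 1 sends the taper urines of weeks 2-3 to a GLIMMIX model. For two further questions, return on day 1 of week 4 and eligibility for oral naltrexone (opioid-negative or opioid-positive urine), "we will build 2 X 2 contingency tables using percentages of participants in the GBP vs. placebo groups". No covariate is named. Section 8 of the Protocol has the same text.

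**Sample size.** The power statement concerns "a difference in the percentage of participants with opioid-free urines at the end of detox as well as immediately prior to initiating NTX therapy", which "will be detected with >90% power with an analysis sample size of 106 total participants anticipated to remain for NTX transition".

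**Adjustment.** There are three routes:
- Data Analysis Methods allows stratified tables, or added model terms, for variables that prove to influence outcome.
- Specific Aim 1 adds a variable to the HLM if the arms differ significantly on it at baseline.
- Specific Aim 3 adds candidate predictors to log-linear and HLM analyses. Its list opens: "Predictors of treatment efficacy during each phase will be examined using baseline assessments (e.g., sex, level of opioid use, distress tolerance" scores, and so on.

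**Data.** Protocol Table 1 schedules both the urine screen and Weekly Drug Use at Pre-TX. Section 7.I describes Weekly Drug Use as an instrument "which uses a timeline recall method that we developed in previous studies to assess self-reported use of opioids and other drugs". Gabapentin or placebo starts on day 3 of week 1 (section 7.C), so the Pre-TX values precede it. The urn variables in section 7.E are withdrawal severity, marijuana use, anxiety and tobacco use, applied separately by sex and prescribed psychoactive medication. Opioid use is not among them.

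**The concern.** The trial's outcome is illicit opioid use, and it holds a measure of the same behaviour from before treatment. Such a measure is usually among the better candidates for a covariate. If it predicts outcome, adjusting for it narrows the interval around the arm difference and corrects for chance imbalance.

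The plan leaves this to triggers. A baseline significance test is a poor one. Under randomisation, a 0.05 test on a variable outside the urn flags a difference in about 1 trial in 20, so the covariate would usually stay out however strongly it predicts outcome. The other trigger, an observed effect on outcome, makes the model depend on the results. Either way the final model for the arm comparison is not known in advance. At stake are some power and a main p-value that does not depend on covariate choices made after the data are seen.

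**Working it through.** **Inputs**
- Two-sided 0.05: the SAP fixes the level and adds "and all tests are two-tailed".
- 106 analysed (SAP, Sample Size). The allocation ratio is not stated; 1:1, or 53 per arm, is assumed.
- 150 enter detox: "Given our expected sample size of 150 participants entering the BUP detox phase". Implied loss is 1 - 106/150 = 29.3%.
- Response rates: "Based on the proportion of participants in the GBP versus placebo groups having opioid-free urines on the last day of the BUP taper" in the pilot, but the proportions themselves are not in the documents.
- Within-arm correlation r between pre-treatment use and the opioid-free outcome: not given; assumed 0.1 to 0.5.

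**The plan's own figure.** Without the pilot proportions, the >90% cannot be reproduced. What can be computed is the difference that gives 90% power with 53 per arm (pooled-variance test, no continuity correction): about 20% against 49%, 30% against 61%, 40% against 71%, or 50% against 80% opioid-free. That is a gap of about 29 to 31 points.

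**Effect of adjustment.** A covariate with correlation r leaves a fraction 1 - r² of the outcome variance, so the standardised effect is divided by √(1 - r²):

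adjusted power = Φ[(1.960 + 1.282)/√(1 - r²) - 1.960], starting from 90%

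equivalent unadjusted N = 106/(1 - r²)

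For r = 0.3: 3.242/0.954 = 3.398; 3.398 - 1.960 = 1.438; Φ(1.438) = 0.925.

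| Assumed r | Power after adjustment | Gain (points) | Equivalent unadjusted N |
|---|---|---|---|
| 0.1 | 90.3% | 0.3 | 107 |
| 0.2 | 91.1% | 1.1 | 110 |
| 0.3 | 92.5% | 2.5 | 116 |
| 0.4 | 94.3% | 4.3 | 126 |
| 0.5 | 96.3% | 6.3 | 141 |

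A gain of 5 points needs r of about 0.44.

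**Check by simulation.** Trials with 53 per arm were simulated 2,500 times per setting, comparing an unadjusted chi-square test with a logistic likelihood-ratio test that has one continuous covariate.
- At 30% against 60.7%, power went from 89.0% to 90.4% (r about 0.21), 89.4% to 93.2% (0.32) and 90.5% to 96.4% (0.45).
- At 40% against 70.7%, it went from 88.2% to 90.1% (0.20), 89.2% to 92.6% (0.32) and 89.6% to 96.1% (0.45).
- Under no arm difference, the adjusted test rejected in 5.5% and 5.8% of trials and the unadjusted test in 5.0% and 4.7% (simulation error about 0.4 points). A small part of the simulated gain may come from that; the formula figures do not depend on it.

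**The longitudinal model.** In a six-visit simulation with N = 150 (4,000 runs, assumed random-intercept SD 1.8 and slope SD 1), the arm-by-time slope test moved from 77.2% to 76.8%, which is no gain. The arm-average test moved from 80.7% to 89.6% at an observed r of about 0.48. That starts near 80% and is not the plan's stated power, so it shows only where the benefit falls.

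**The case against.** Much of the case on the other side stands, and it limits what can be claimed.

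A reader might infer that the plan ignores prior opioid use. It does not: stratified tables, HLM cofactors and the Aim 3 models could all bring it in. The fault is that none of these routes is fixed in advance for the Aim 1 arm comparison.

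A reader might also infer that the whole powered comparison is a crude table. Only the half just before naltrexone is. Urines at the end of the taper go into GLIMMIX, and the declared primary outcome is change across detoxification. For a pure slope test of that change, the adjustment adds nothing to power.

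A third inference would be that the result is biased or the test invalid. Nothing supports that. Randomisation balances opioid use in expectation, and the urn balances withdrawal severity, which is plausibly related. The unadjusted table is a valid test, subject to dropout, which this covariate would not by itself repair.

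Finally, the size rests on a correlation the documents do not give. Everyone enrolled has moderate to severe opioid use disorder, so the range of prior use may be narrow and r low. Weekly Drug Use also has no stated score or unit, so calling it continuous requires a definition first.

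None of this answers the remaining point: the covariate is available before treatment, the SAP considers it a plausible predictor, and its use in the main comparison is left open.

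**Conclusion.** The concern holds as a low-cost improvement: the plan should fix adjustment for pre-treatment opioid use in advance. The likely gain on the comparison before naltrexone is 0.3 to 6.3 points of power from a base of 90% at N = 106, for r between 0.1 and 0.5. It is about 1 point or less if r is 0.2 or lower. This assumes 1:1 allocation, that the stated power is right, and a correlation nobody can read from the documents.

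The documents do not support a claim of substantial lost power on the declared primary outcome. The benefit lies in the percentage and arm-average comparisons, and in removing a covariate choice that would otherwise depend on the data.

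**What to change.** - Define one continuous Pre-TX opioid-use score from Weekly Drug Use, for example days of use in the recall window, and state the window. A Pre-TX urine result is likely to be positive in nearly everyone (an assumption) and would then carry little information.
- For the opioid-negative comparison on day 1 of week 4, prespecify a logistic regression on arm plus that score. Report the standardised risk difference with its interval, and name the test in advance. Keep the 2 X 2 table as description.
- Enter the same score as a fixed covariate in the Aim 1 GLIMMIX urine model, regardless of any baseline significance test.
- Withdraw the data-triggered adjustment rules for these two analyses, or label them as sensitivity analyses.

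The cost is SAP wording, the choice of score, and one parameter per model. The data are already scheduled for collection. The change should be made before the arm comparison is seen.

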During the detox phase, morning GBP/placebo ingestion will occur under supervision 6 days per week, and a take-home dose will be given each day for evening ingestion (3 take-home doses on Sat to also cover Sun). For participants on the truncated schedule due to COVID-19 (thrice weekly), lockboxes with BUP and GBP/Placebo will be given on the same schedule to be taken on days when not presenting to clinic (Tues, Thurs, weekends) with specific instructions provided by CAST nurse, in addition to drug accountability logs signed by the participant. Additional take-home doses of GBP/placebo will be given to take on holidays, days when clinic is closed due to inclement weather and holidays to ensure adequate blood levels of GBP are maintained. The initial dose of GBP at 100 mg will be given on day 3 of week 1, and a 100 mg dose provided to take home. The GBP dose will increase to 200 mg BID on day 4, 400 mg BID on day 5, 600 mg BID on day 6, and 800 mg BID (1,600 mg/day) on day 7 of week 1. Participants will remain on 1600 mg/day through day 2 of week 5 (during NTX therapy, GBP/placebo capsules will be given in weekly blister packs). Then GBP will be reduced to 1200 mg/day on day 3, 800 mg/day on day 4, 600 mg on day 5, 400 mg on day 6, and 200 mg on day 7. On days 1 and 2 of week 6, all participants will receive placebo. If GBP side effects are too severe at the 800-mg BID dose, GBP will be decreased to no less than 1200 mg/day, given data that 900 mg/day of GBP is ineffective [97]. If GBP side effects are too severe at 1200 mg/day, GBP will be discontinued and the participant will be discharged from the study and referred to local treatment agencies. During transition to NTX (week 4), if a) the participant's urine sample is opioid-negative and/or regular opioid use is not indicated, *and* b) orthostatic vital signs and symptoms are within limits specified below (Section 14, Protection of Participants, B. Protections Against Risk): On day 1 of week 4, participants will receive 0.1 mg of clonidine followed 20-30 min later by 6.25 mg of oral NTX. If tolerated, the person will return on day 2, receive 0.1 mg of clonidine followed 20-30 min later by 6.25 mg of oral NTX. On day 3, participants will receive 12.5 mg of NTX 20-30 min after clonidine. (For those who do not start induction until day 2 or 3: Starting on day 2, NTX will be given at the 6.25 mg dose 20-30 min after clonidine. On day 3, NTX will be given at the 12.5 mg dose 20-30 min after clonidine.) On day 4, 25 mg of NTX will be given 20-30 min after clonidine. If 25 mg is tolerated, then on the morning of day 5, participants will receive the depot NTX injection. (Participants have up to day 3 of week 4 to start the transition to NTX. For those who do not start induction until day 2 or 3: Starting on day 2, NTX will be given at the 6.25 mg dose 20-30 min after clonidine. Starting on day 3, NTX will be given at the 12.5 mg dose 20-30 min after clonidine. In such cases, dosing/administration on subsequent days will be as specified above.) Those

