- H. **Program Termination** - Any participant choosing not to take the study medication will be discharged from the study with appropriate referrals. During the detox phase and NTX transition week, participants missing medications on three successive days (or any two days during week 1) or do not complete assessments will be administratively discharged. If participating under the truncated schedule due to COVID-19, participants will be discharged if they miss any clinic visits during week 1 and miss 1 clinic day during weeks 2 and 3 due to the take-home medication schedule, therefore, they cannot miss Friday visits. Participants will be discharged if they do not receive their take-home medication blister packs by day 5 of week 4. Participants who cannot provide an opioid-free urine on either day 1, 2, or 3 of week 4 during oral NTX induction may be deemed ineligible to continue onto depot NTX therapy as determined by the study physician. Similarly, if participants are unable to provide an opioid-free urine at the week 8 visit, a study physician will determine if participants will be eligible to continue in the study with or without the second NTX injection. A participant will be discharged if PIs believe a subject's health or wellbeing may be threatened by continuation in the study. If a participant is required to quarantine due to COVID-19 during the phase I BUP detox, they will be discharged from the protocol, and the study physician will provide take-home BUP taper for detox. If a participant is required to quarantine due to COVID-19 during phase II, they may remain on protocol and complete assessments and therapy sessions remotely (by phone or teleconference). If this occurs, they will be unable to provide urine drug screens or complete the COWS assessment until they are no longer required to quarantine. If a participant is unable to provide a urine drug screen at week 8 due to quarantine, they will not be eligible for the second Vivitrol injection and will be discharged from protocol and offered referrals to treatment as necessary. If a pregnancy test becomes positive, the participant will be withdrawn from the study and referred to an appropriate treatment program. Participants who relapse following BUP detox or NTX therapy, as determined by physician assessment, will be offered referrals to the UAMS Center for Addiction Services and Treatment, a residential therapeutic community, an inpatient treatment program, or others, as appropriate. Participants administratively discharged will also be referred to local treatment programs, if desired.

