occurred during gabapentin induction that were at least possibly study-related and showed a greater incidence in the gabapentin than placebo group: nausea/vomiting (gabapentin: N=2/16; placebo: N=1/14), somnolence (gabapentin: N=2/16; placebo: N=0/14), sleep disturbances (gabapentin: N=2/16; placebo: N=0/14), loss of motor skills (gabapentin: N=1/16; placebo: N=0/14), and lightheadedness (gabapentin: N=1/16; placebo: N=0/14). All events were mild and did not require an intervention, except for the lightheadedness, which occurred on day 4 during induction onto gabapentin. Even though vital signs were within the normal range, because this was a pilot study, a conservative approach was used and the gabapentin induction discontinued for this participant. Thus, we anticipate no pharmacokinetic interactions between these agents. There has also been one case study looking at gabapentin and buprenorphine and there was no adverse reaction. This case study was based on a previous 2006 review that showed that gabapentin produced a decrease in opioids consumed postoperatively [166, 167]. Nevertheless, based on the 12/19/19 safety report by the FDA, serious breathing difficulties may occur as a result of combined use of gabapentin and opioid pain medicines.

5. Clonidine. The use of clonidine to alleviate symptoms of opioid withdrawal is a standard clinical practice. Clonidine produces side effects such as dry mouth, drowsiness, sedation, dizziness, headache, fatigue, and changes in heart rate and blood pressure. The dose employed is within the recommended daily dose range [168].

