Statistical Analysis Plan

Study Title: Improving Treatment Outcomes for Prescription Opioid Dependence

NCT Number: NCT02543944

Date last reviewed by IRB: 10/4/2021

Data Analysis Methods:

We will compare baseline characteristics of the two groups using the intent-to-treat sample with analyses of variance for continuous variables (e.g., age) and Chi² analyses for categorical variables (e.g., sex, race) to determine whether any significant baseline differences have accrued despite randomization. In addition, given that later phases (i.e., transition, depot NTX therapy) may have different sample configurations due to anticipated dropout, we will similarly compare the two groups on participant characteristics. If we find significant baseline differences in variables within a phase or at each subsequent phase relative to the one prior, these differences will be informative of factors associated with treatment outcomes. For those variables found to affect outcome, we will use contingency tables with stratification or add these factors to the appropriate random regression models to adjust for these differences.

Our primary outcome is changes in opioid positive urines over time during the detox phase. Other major outcomes are: percentage of detox phase completers, naltrexone phase initiators and vivitrol receivers.

Specific Aim 1: Efficacy and tolerability of GBP versus Placebo during and immediately following BUP detox.

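### The two week-4 GBP-versus-placebo tables compare taper completers and, apparently, returners only; no stated analysis compares the randomised arms on reaching week 4 opioid-negative

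*SAP*

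**What the plan says.** SAP, Specific Aim 1 (same text in Protocol Section 8) asks whether the arms differ in retention into the naltrexone (NTX) transition and in eligibility for oral induction. It answers with two tables by arm, contrasting those who "return on day 1 of week 4 versus drop out after completing the taper, and 2) test negative versus positive for opioids". Both outcomes in the first table belong to people who finished the taper. The second states no denominator. The same section uses available data without filling in missing values.

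SAP, Sample Size bases power for the urine comparison on "an analysis sample size of 106 total participants anticipated to remain for NTX transition". Its pilot input was formed by "treating the one missing value as positive", but no such rule is given for the trial's own table. The intent-to-treat sample is named for the baseline comparison and in this paragraph, not for the week-4 tables.

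On timing, Protocol Section 7.C says: "The initial dose of GBP at 100 mg will be given on day 3 of week 1". Exits before week 4 can follow from the study drug: "If GBP side effects are too severe at 1200 mg/day, GBP will be discontinued and the participant will be discharged from the study". Section 7.H adds discharge for missed medication.

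Four other provisions matter:
- Kaplan-Meier comparison of retention among taper starters, and a separate look at dropout during GBP induction.
- Adjustment for measured factors: "For those variables found to affect outcome, we will use contingency tables with stratification".
- Percentages of detox completers, NTX initiators and Vivitrol receivers (SAP, Data Analysis Methods) and a GBP-versus-placebo induction table (Specific Aim 2), all without a stated denominator.
- A week-16 ANOVA (Longer-Term Outcomes) with arm and three post-randomisation success indicators as factors.

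**The concern.** Randomisation makes the arms comparable on the day it is done. A table restricted to people who finished the taper, or who came back with a sample, compares groups that the study drug may already have shaped. If GBP keeps in treatment people who would otherwise have left, and those people are more likely to be using opioids, GBP looks worse among returners. If GBP drives out people who were struggling, it looks better.

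At stake is what can be said about GBP and access to naltrexone. These are the plan's stated comparisons of retention to, and eligibility for, the transition. As written, a reader cannot tell whether a difference, or its absence, describes everyone randomised or only those who stayed.

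**Working it through.** **Inputs.** From SAP, Sample Size: 150 entering, 106 remaining, power above 90%. From Specific Aim 1: two-sided alpha 0.05. Assumed: all 150 are randomised, 1:1, so 75 per arm (the ratio is not stated). Retention by arm and the pilot urine rates are not in the documents.

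**Expected loss.** 150 − 106 = 44, and 44/150 = 29.3%. This reads 106 as those who remain. The same paragraph later calls the 106 eligible for transition, but the power sentence supports the first reading.

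**The plan's own power.** It cannot be reproduced without the pilot rates. With 53 per arm, 90% power requires, for example, 30% v 61% or 50% v 80% opioid-free.

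**Table 2 among returners.** Let 57/75 GBP (76%) and 49/75 placebo (65%) return, 106 in all, with 30 placebo returners negative (30/49 = 61.2%; 30/75 = 40% of the arm). GBP then has 57 − 49 = 8 extra returners. Vary how many of the 8 are negative. The test is an uncorrected chi-square; rejection rates are from simulation.

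| Extra returners negative | GBP, returners | GBP, all randomised | Table 2 rejects |
|---|---|---|---|
| none | 30/57 = 52.6% | 30/75 = 40.0% | 14% |
| a quarter (2) | 32/57 = 56.1% | 32/75 = 42.7% | 8% |
| half (4) | 34/57 = 59.6% | 34/75 = 45.3% | 5% |
| at the placebo rate (4.9) | 61.2% | 46.5% | 5% |

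Hand check of row one: the difference is −0.086; the pooled rate is 60/106 = 0.566; SE = √[0.566 × 0.434 × (1/57 + 1/49)] = 0.0966; so the mean z is −0.89. The chance that |z| exceeds 1.96 is about 14%.

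Only in row one are the randomised arms truly equal, so only its 14% is a false-positive rate against the all-randomised null. In rows two and three GBP is ahead among all randomised, yet most rejections go against it. In the last row there is no bias.

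At 60/75 v 46/75 (80% v 61%) the four figures are 35%, 16%, 7% and 5%. With retention reversed (61% v 80%) and none of the extra placebo returners negative, Table 2 rejects 35%, essentially all in favour of GBP. Equal retention with equal urine rates gives 5%.

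**Table 1.** If 84% v 73% complete the taper and 90% of completers return in each arm, returns are 76% v 65% of those randomised. Table 1 rejects 5%, which is correct for its own step. An all-randomised test of return rejects 29%. With 89% v 68% completing, the figures are 5% and 72%. The Kaplan-Meier analyses address this earlier loss; Table 1 does not.

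**Power of an all-randomised version.** For each placebo rate p₀ among returners, take the GBP rate p₁ that gives 90% power at 53 per arm. Multiply both by 106/150 = 0.707 (equal retention) and recompute at 75 per arm:

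Power = Φ{(|p₁ − p₀| − 1.96·√[2p̄(1 − p̄)/n]) / √[(p₁(1 − p₁) + p₀(1 − p₀))/n]}

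| p₀ v p₁, returners | All randomised | Power, 75 per arm |
|---|---|---|
| 10% v 36.0% | 7.1% v 25.4% | 87% |
| 30% v 60.7% | 21.2% v 42.9% | 82% |
| 50% v 79.5% | 35.3% v 56.2% | 73% |
| 60% v 87.2% | 42.4% v 61.6% | 66% |

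For the 30% row: (0.217 − 1.96 × 0.0762)/0.0741 = 0.91, and Φ(0.91) = 82%.

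**Week 16.** No arithmetic applies. The three success indicators arise after randomisation and may be affected by GBP. The arm term fitted beside them is a conditional contrast, not the overall effect of GBP.

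**The case against.** The best defence has four parts.

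First, retention is already compared by arm: the Kaplan-Meier analyses cover taper starters and, separately, GBP induction. This stands. A reader might infer that the plan never compares loss in weeks 1 to 3; the SAP does not support that. What remains uncovered is urine status, and retention is split across two sets.

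Second, Table 1 asks about the step from detox to transition and answers it correctly. This stands too; the table is not wrong for its own question.

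Third, the completer, initiator and Vivitrol percentages and the induction table have open denominators and could be run on whole arms. A reader might infer that the plan excludes all-randomised analysis; it leaves the denominator unsaid. But leaving it unsaid does not supply an all-randomised week-4 result, and Specific Aim 2's descriptive induction rate is among abstinent participants only.

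Fourth, the bias figures are hypothetical. Discharge rules apply to both arms under blinding, and the pilot evidence of drug-related exit is one of 16 GBP participants, for whom "a conservative approach was used and the gabapentin induction discontinued for this participant"; it comes from a list confined to events commoner on GBP. This also stands: it shows a mechanism, not a rate. A reader might take 14% or 35% as estimates of error in this trial. They are not, since they need every extra returner to be opioid-positive. Differential retention alone does not bias Table 2; the mix of returners must differ.

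The planned stratification helps only as far as measured factors identify the extra returners.

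**Conclusion.** The point holds as a gap that should be fixed in two secondary tables. Table 1's restriction is explicit. Table 2's is inferred from the absent cell, the available-data rule and the power basis of 106. No stated analysis compares the randomised arms on returning at week 4 opioid-negative, and 29% are expected to be lost by then.

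The size of any bias in Table 2 cannot be known from the documents. With 75 per arm, 76% v 65% retention and 40% of the placebo arm returning and negative, it rejects between 5% and 14%, in a direction that depends on which arm retains more people.

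Two stronger conclusions do not follow. The primary outcome, change in opioid-positive urines during detox, is not affected in this way. And the week-16 ANOVA is not invalid: it suits the prognostic aim. Nor can one say that adjustment there removes exactly the part of the GBP effect that passes through those steps, because conditioning on post-randomisation success can leave bias or add it. The arm term simply does not estimate the overall effect.

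**What to change.** For both week-4 tables, add a version with all randomised participants per arm as denominator. Count as not achieved anyone who does not return on day 1 of week 4 or, for the second table, has no opioid-negative sample that day. Label the second a composite of retention and urine result. Use the same denominator for the Specific Aim 2 induction table and for the completer, initiator and Vivitrol percentages. Keep the completer-only and returner-only tables as labelled descriptive analyses. A version using the protocol's induction window (up to day 3 of week 4, Sections 7.B and 7.C) may be added as a sensitivity analysis; it is a different endpoint from the day-1 assessment.

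Separately, at week 16 add a comparison of arms without the success factors, and keep the existing ANOVA as prognostic.

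The cost is SAP wording and a few tables, with no new data. Percentages will fall. With equal retention, power drops from 90% to about 66% to 87%, so the stated power above 90% should be described as applying to the returners-only comparison. Regaining 90% would take 83 to 140 per arm over the same range of rates. The question also changes: with the same urine rate among returners in both arms, the composite rejects 14% at 76% v 65% retention and 34% at 80% v 61%. That is a retention effect and must be reported as one.
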